**CDC Check for Safety Check list:**

Participants in the MACRO Intervention arm may receive a Home Fall Prevention Checklist for Older Adults. This check list will be utilized to provide the participant the opportunity to be better informed about safety. The check list may be sent when direct home assessments are not completed.

**MACRO De-Prescribing:** All participants in MACRO will have their medications reviewed to identify DEMS (deprescribing eligible medications). DEMs worsen functional recovery, impair cognitive function, and increase medical risks (falls, bleeding). For participants in the MACRO Intervention arm, opportunities for de-prescribing will be reviewed and specific recommendations will be conveyed to the participant's clinician to optimize recovery (optimizing physical function, minimizing confusion, reducing falls).

Deprescribing assessments will be conducted during the baseline assessments as part of a medication review. Communication will then be initiated with the MACRO participant's primary provider. DEMs have been selected based on goals to optimize function, reduced sedation, and minimize falls.

If DEMS are deprescribed, a standardized approach of follow-up assessments will be implemented to ensure deprescription is well tolerated.

**MACRO arm personalized nutrition:** Older CVD patients are particularly prone to sarcopenia, frailty, and associated vulnerabilities such as exercise intolerance, falls, and poor QOL. A high-quality diet and increased protein intake have been shown to be advantageous in these vulnerable adults. The MACRO Intervention participants will be strongly encouraged to meet with a registered dietitian and receive dietary recommendations that will account for sarcopenia, underweight, overweight, and specific dietary restrictions associated with comorbid conditions (e.g., DM, renal disease) and medications. Nutrition education and facilitation will be optimized in MACRO. The MACRO Intervention participants will be strongly encouraged to meet with a registered dietitian and receive dietary recommendations that will account for sarcopenia, underweight, overweight, and specific dietary restrictions associated with comorbid conditions (e.g., DM, renal disease) and medications. Nutrition education and facilitation will be optimized in MACRO.

**MACRO Intervention arm telephone intervention.** MACRO staff will contact participants randomized to the MACRO arm approximately once each week until the completion of phase II after which approximately monthly phone calls will be completed. A subset of telephone calls will have a second MACRO staff member listening to calls to enable additional monitoring. The components of each session recorded on the checklist.

### **7.3 Quality Assurance**

- A. **Fidelity** refers to whether team members consistently perform the MACRO intervention with a high level of adherence to and competence with the intervention protocol. Low fidelity is a common and often unrecognized problem leading to “failed” intervention studies. We will apply expertise from numerous intervention studies, including multi-site studies: (1) Attaining fidelity – we will train team members at each site. (2) Measuring and maintaining fidelity – Co-investigators will have regular supervisory calls with team members. Their intervention sessions may be randomly sampled by the supervisors and rated according to meeting fidelity standards. The PIs are the ultimate fidelity supervisors; they will be in regular contact with the supervisors, study coordinators, and research assistants to promptly detect and correct problems. Such training and monitoring have been successful in our recent rehabilitation studies.
- B. **Interventionist training and certification.** Prior to beginning the study, the research staff will be trained on the intervention. Regular telephone calls will be held with intervention research staff to discuss problem participants or challenging issues that arise in the delivery of the intervention.
- C. **SOC control group.** The SOC group controls for the possibility that regular contact with the study team may improve outcomes in participants randomized to the intervention. Participants randomized to the SOC group will follow the standard hospital process and may or may not receive CR.
- D. **Quality control of outcome measures.** All research study staff will be trained in each aspect of the study that they are involved in. Training will be completed by subject matter experts in the specific area within the research team. Data will be reviewed for quality control, standardization, and abnormalities in collection and will be discussed at regular meetings.

### **7.4 Procedures performed to lessen the probability or magnitude of risks.**

In the event that in-person assessments or interventions become infeasible (e.g., COVID 19 outbreak), the researchers will carry out these study components remotely (i.e., by telephone, mail, email, Redcap, e-consent, or video call).

- A. Adequacy of protection against risks and methods to minimize potential risks.**  
Overview of protection against risks. Research staff is trained in each element of the study visit they will perform; including obtaining informed consent, administering questionnaires, protecting confidentiality of collected data, performing the frail assessment. Additional training will be provided as needed.
- B. Minimizing risks related to assessments.** If a participant develops symptoms such as chest discomfort, new dyspnea, new fatigue, study staff will notify hospital or facility staff, or the study cardiologist.
- C. Staff Training.** All research staff will undergo training and certification prior to working with participants and will re-certify as necessary every 12 months to ensure continued adherence to study protocol.
- D. Minimizing risk related to loss of confidentiality.** The following methods will be employed to maintain confidentiality of participants. Research staff members have completed training in the ethical conduct of human subject research, including maintaining participant confidentiality. Only study investigators and research staff will have access to the study database. Participants will be assigned a unique study identifier. Individual names will ultimately be removed from the study database and only the unique study identifier will be used to distinguish participants in the database. Data will be maintained in computer files and file cabinets to which only the study staff have access. Collected data will be used only for research purposes. Any published data will not contain any individual identifiers.
- E. Minimizing risk related to loss of confidentiality during intervention.** Participation includes a risk of loss of confidentiality regarding personal health information. However, all research staff have undergone formal human subjects training. They are trained to protect the privacy of research subject participants.
- F. Data and Safety Monitoring Board (DSMB).** The DSMB will meet approximately every six months or as decided by the DSMB. The DSMB will meet to review and approve the protocol prior to beginning data collection. They will decide on specific stopping criteria for the study. The biostatistician and data manager will work closely with the DSMB to provide reports in an acceptable format. Serious Adverse events (SAE) / Adverse events will be monitored continuously throughout the study and will be reported to the DSMB and IRB according to pre-specified requirements. SAE/AE rates and interim study results will be reviewed and discussed by the DSMB at the DSMB meetings.

## **7.5     *Source records that will be used.***

Sources of material. Primary and secondary outcome measures that will be collected for this study include the AM-PAC CAT, accelerometry, cognitive assessment, depression, frailty, IADLs, readiness for change, adherence, self-efficacy, falls, medication assessment, readmissions, institutionalization.

## **8.0     *Data Storage***

### **8.1     *Data to be stored***

Data at the active sites will be coded; meaning that a key will exist that can link the codes back to the direct subject identifiers. Each participant will be assigned a unique study ID number that can be traced back to the study participant. Data provided to the coordinating center will be de-identified.

## **8.2 Procedures to release data.**

Only the local site PI has control over release of study data. Any investigators seeking to analyze data must contact the site PI for permission. Each request, if it occurs, will be considered on a case-by-case basis and will require obtaining IRB approval prior to releasing.

# **9.0 Data Management**

## **9.1 Data analysis plan.**

A. **Data management.** Data management staff will coordinate the data oversight under the direction of [name] study statistician for all sites and will utilize the insight form the University of Pittsburgh Physical Therapy Data Center for Data Management.

B. **Data Safety Monitoring Board (DSMB).**

The DSMB will also be expected to meet as needed, but not less than, every six months to provide an overall summary status report to the regulatory agencies. An emergency meeting of the DSMB may be called at any time by the Chair should participant safety questions or other unanticipated problems arise.

In addition, the DSMB Report addressing the following information will be submitted to the IRB at the time of continuing review annually or more often as required:

- A list of the research personnel who participated in the data and safety monitoring.
- The frequency of monitoring that took place during the renewal intervals and/or the dates that data and safety monitoring was conducted.
- A summary of cumulative data related to unanticipated problems (including adverse events) including a determination of causality and whether the risk to benefit assessment has changed.
- If appropriate, a summary of pertinent scientific literature reports, therapeutic developments, or results of related studies that may have an impact on the safety of study participants or the ethics of the research study.
- A summary of the outcome of reviews conducted to ensure subject privacy and research data confidentiality.

Final conclusions regarding changes to the anticipated benefit-to-risk assessment of the study participation and final recommendations related to continuing, changing, or terminating the study.

C. **Statistical Analyses.** Overview-We will perform all main analysis based on intention-to-treat philosophy following the a priori plans outlined below. All statistical analyses will be performed and overseen by the study statistician [name] using SAS® version 9 (SAS Institute, Inc., Cary, North Carolina). Participant flow will be summarized using a CONSORT diagram. Data will be summarized by treatment group and time point as well as baseline to follow-up change using appropriate descriptive statistics. First, the baseline participant characteristics will be compared between the two arms. Any significant differences will be noted and accounted for as additional covariates in the sensitivity analyses. Second, main analyses to address the aims will be performed as outlined below. Confirmatory hypothesis testing will be performed using multiple imputation for missing data. Third, a set of sensitivity analyses including additional covariates and ignoring missing data will be performed to evaluate the robustness of our findings.

**Baseline Comparisons**-Due to the randomization scheme balanced with respect to study site and the large sample size, it is unlikely that other baseline participant characteristics will be significantly different between the arms. However, we will control for any participant characteristics that are found to be significantly different by including them as additional covariates in the sensitivity analyses. In such an event, we will not alter the primary analytic strategy to preserve its a priori nature and predictability. We will use independent samples *t*-, Wilcoxon rank sum, chi-square and Fisher's exact tests, as appropriate based on distributional properties, and continuous/categorical nature of the characteristic being compared.

**Aim 1 Analysis**-We will fit a series of linear mixed models using the SAS® MIXED procedure with baseline to follow-up changes in continuous outcomes as the dependent variable; intervention arm (MACRO/SOC), follow-up time point (3/6/12 months) and their interaction term as the fixed effects of interest; the baseline value of the continuous outcome as a fixed effect covariate; and a participant random effect to account for multiple measurements over time from the same participant. We will appropriately construct means contrasts to estimate MACRO vs SOC at each follow-up time point. The magnitude and statistical significance at  $\alpha=0.05$  of the MACRO vs SOC difference at 3 months for AM-PAC CAT Basic Mobility Domain will serve as the formal test of the primary hypothesis H1.1. If significant, we will define a meaningful responder as having at least a 2.60 point improvement in AM-PAC CAT Basic Mobility Domain over 3 months, compute percentage of responders in both arms, and conclude a number-needed-to-treat (NNT) as the reciprocal of the difference in percentages. We will employ the same analytic strategy described above for each of our secondary continuous outcomes such as physical activity, depression, frailty, self-efficacy and quality of life (H1.2). For the secondary outcomes measured only once at 3 months such as participation, adherence and satisfaction (H1.3), we will consider using Wilcoxon rank sum, chi-square and Fisher's exact tests to make between-intervention comparisons, depending on the categorical/ordinal/interval nature of the outcomes and their propensity for ill-behaved distributional properties. For count outcomes such as falls, number of medications, readmissions and hospitalizations in H1.4, we will fit a series of negative binomial regression models with the count outcome as the dependent variable; exposure time for the counts as an offset; a log link function; and intervention arm as the main independent factor of interest; and a marker of history of the outcome at baseline as a covariate MACRO vs SOC incident rate ratio and its statistical significance will serve as tests of H1.4.

**Aim 2 Analysis**-In the linear mixed models described above for H1.1 and H1.2, we will examine the between-intervention means contrasts at 6- and 12-months. The magnitude and statistical significance of the MACRO vs SOC arm differences at 6 and 12 months will serve as the formal test of the hypothesis H2.1.

**Aim 3 Analysis**- We will examine characteristics of patients likely to reap the greatest benefits from MACRO compared to SOC arms and will be accomplished through exploratory subgroup analyses. We will examine subgroups based on baseline AM-PAC CAT Basic Mobility Scale, frailty status, cognitive function, and readiness for change. Specifically, for each subgroup definition considered, we will add subgroup and subgroup  $\times$  intervention group interaction terms to the models used in Aims 1 and 2. If the interaction terms are statistically significant, we will make subgroup-specific between-intervention comparisons.

Our second avenue of exploration would be to delineate characteristics of patients most/least likely to reap benefits from the MACRO intervention. Specifically, we will only use the data from the MACRO arm, and define a meaningful responder as having a 3-month improvement of at least 2.60 points in AM-PAC CAT Basic Mobility Scale. First, we will compare the baseline characteristics of

responders and non-responders using methods described above. Second, we will fit logistic regression models with responder status (yes/no) as the dependent variable, and each of the baseline characteristics, one-at-a-time, as the sole independent variable to identify which factors are likely to be relevant. Third, we will fit a multivariable logistic regression model with all relevant baseline characteristics as independent variables, and a forward selection strategy to potentially identify a parsimonious collection of relevant baseline characteristics predictive of likelihood of benefit. Finally, to better accommodate non-linear associations and interaction effects among baseline characteristics, we will consider a classification tree model or CART.

**Missing Data**-The best approach for handling missing data is prevention, and our clinical trials have had a low missingness rate. We will clearly document missing data and reasons in the CONSORT diagram and compare those with missing data to complete data at the follow-up assessments using the same methods outlined under *Baseline Comparisons* subsection above. We will use methods such as multiple imputation which consider the uncertainty involved in imputing missing data. Multiple imputation is arguably the best method to account for missing data under the ignorable or missing-at-random (MAR) assumption, and mitigates bias even when missing data is non-ignorable. Specifically, we will generate M=5 imputed values for each missing value, analyze the 5 datasets as though complete, and finally combine the results appropriately so that they reflect the uncertainty involved in imputation. SAS® MI and MIANALYZE procedures will be used. Other approaches to missing data will also be considered in sensitivity analyses.

**Sensitivity Analyses**-We will perform sensitivity analyses to examine the robustness of our results against various assumptions, such as fitting zero-inflated models or using dichotomous (any/none) operational definitions and logistic regression models. In addition, if analyses of residuals from the linear mixed models show violations of statistical assumptions, we will consider fitting models after Box-Cox transforming the continuous variables to make them approximately conform to a normal distribution.

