#### D. Sample Size and Power.

**Sample Size Justification.** We base our sample size on published data, published statistical methods, and commercially available software (SAS® POWER procedure; SAS Institute, Inc., Cary, North Carolina). Between-subject standard deviation of the baseline to follow-up change in the primary outcome AM-PAC CAT Basic Mobility Scale is approximately 7.97 in rehabilitation outpatients. We consider 2.60 points a minimally clinically important difference based on MDC68. We plan to randomize 187+187=374 participants, anticipating 149+149 completers assuming a conservative 80% retention rate. We can detect a between treatment arm difference of 2.60 points in AM-PAC CAT Basic Mobility Scale with 80% statistical power in a two-tailed test at  $\alpha=0.05$ . This difference is smaller than the actual observed changes previously reported, indicating ample statistical sensitivity. The logistic regression model proposed in Aim 3 requires a minimum of about 5-10 events per variable, and assuming a half in the MACRO group responds, we would be able to fit a multivariable model with at least 15 variables. Thus, we are confident of the adequacy of sample size to address all aims.

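### Covariates for one sensitivity analysis are chosen by baseline significance tests, and the plan wrongly gives sample size as a reason to expect few positive tests

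*Combined protocol and SAP*

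**What the plan says.** The rule appears twice in Section 9.1 C. The overview says: "Any significant differences will be noted and accounted for as additional covariates in the sensitivity analyses". The Baseline Comparisons paragraph repeats it: "we will control for any participant characteristics that are found to be significantly different by including them as additional covariates in the sensitivity analyses". The tests are t, rank sum, chi-square or Fisher tests, according to the type of variable.

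The plan expects few positives and gives two reasons: "Due to the randomization scheme balanced with respect to study site and the large sample size", it says, "it is unlikely that other baseline participant characteristics will be significantly different between the arms".

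The same paragraph limits the reach of the rule. If differences are found, "we will not alter the primary analytic strategy to preserve its a priori nature and predictability".

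For this step the plan gives no list of characteristics, no significance level, no multiplicity rule and no covariates named on prognostic grounds. In the Aim 1 mixed model the only baseline covariate is the outcome's own baseline value. The count models carry a baseline marker of the outcome's history.

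**The concern.** Two things look wrong.

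First, the sample-size reason. When allocation is random, any baseline difference is due to chance. A larger trial makes chance differences smaller, but the difference needed for significance shrinks in the same proportion. How often a test is positive does not change.

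Second, the selection rule. Adjusting for a baseline variable helps when that variable predicts the outcome. This rule looks only at whether the variable happened to be imbalanced. It can admit a variable unrelated to mobility and leave out a strong predictor whose imbalance gave p = 0.08. It also means that the adjusted model is unknown until the data are seen. If no test is positive, the rule supplies no covariates at all.

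At stake is how much the covariate-adjusted sensitivity analysis can say about robustness.

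**Working it through.** **Inputs from the documents.** 187+187 = 374 randomized, 149+149 completers, SD of change 7.97, target difference 2.60, two-sided 0.05 and 80% power (Section 9.1 D); 1:1 allocation in small even blocks, stratified by site only (Section 3.1 B).

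**Assumptions.** Baseline tests at 0.05, since 0.05 is stated only for the primary test. Between 10 and 30 characteristics, with 17 as a middle value based on the Section 7.2 assessments plus demographics. For the simulations: four sites, block sizes 2, 4 and 6, normally distributed characteristics.

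**1. The plan's own figure.** It gives no probability for baseline differences, so the related figure to reproduce is the power. n per arm = 2 × (1.960 + 0.842)² × 7.97² / 2.60² = 147.5, so 148. With 149 per arm, power is 0.804 (normal) or 0.801 (noncentral t). The stated 80% is reproduced. The unadjusted standard error is 7.97 × √(2/149) = 0.92.

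**2. Does sample size matter?** In SD units, the chance imbalance of a characteristic has standard deviation √(2/n) with n per arm, and significance needs about 1.96 × √(2/n). The ratio is 1.96 whatever n is.

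| Total N | SD of imbalance | Needed for p<0.05 | Simulated positives per test |
|---|---|---|---|
| 60 | 0.258 | 0.506 | 5.1% |
| 374 | 0.103 | 0.203 | 5.1% |
| 2000 | 0.045 | 0.088 | 4.9% |

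**3. Chance of at least one positive.** For k independent tests this is 1 − 0.95^k:
- k = 10: 40%
- k = 17: 58%
- k = 20: 64%
- k = 30: 79%

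The expected number of positives is 0.05k, so 0.5 to 1.5.

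Dependence and site effects lower these figures. Simulated with k = 17 (1,500 runs each, Monte Carlo error about 1.3 percentage points):
- Pairwise correlation 0.3, no site differences: about 50% at N = 60, 374 and 2000 alike.
- Independent, between-site SD 0.3, N = 374: 53%.
- Correlation 0.3, between-site SD 0.5, N = 374: 37%, with a per-test rate of 3.4%.

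**4. Effect on the sensitivity estimate.** Simulated at 149 per arm with SD 7.97, 17 independent characteristics and one of them correlated r with the outcome (4,000 runs, no true difference). The comparison is with one prespecified prognostic covariate.

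| r | Mean SE, unadjusted | Mean SE, chosen by p<0.05 | Mean SE, prespecified |
|---|---|---|---|
| 0.3 | 0.92 | 0.93 | 0.88 |
| 0.5 | 0.92 | 0.92 | 0.80 |

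The prognostic variable is selected only about 5% of the time. When the rule added covariates, the estimate moved by 0.12 to 0.19 points on average (r from 0 to 0.5). The significance verdict matched the unadjusted one in 98% to 99% of runs with no true difference, and in 96% with a true difference of 2.60 and r = 0.3.

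**The case against.** The strongest reply is that little depends on this rule, and much of that stands.

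- **The primary test is protected.** A reader might infer that data-driven covariates threaten H1.1. They do not: the plan rules out changing the primary strategy, so its estimate, p-value and type I error are untouched.
- **This is not the plan's main robustness check.** A reader might take it for that. Section 9.1 C also lists an analysis ignoring missing data, other missing-data approaches, zero-inflated models, dichotomized outcomes and Box-Cox transformation, and ranks none of them.
- **The models already contain important prognostic information.** It would be too strong to say that the rule leaves out the variables that matter. Every continuous-outcome model adjusts for the baseline outcome value. What can be lost is prognostic information beyond that, so the gains in step 4, which start from an unadjusted SE, may overstate the benefit.
- **Site balance is a partly valid reason.** Section 3.1 B says that the sites differ in key demographics, and stratification lowers the positive rate for characteristics that vary by site. Fisher's exact test is also conservative.
- **For a single characteristic, 5% is indeed unlikely.** The documents do not show that the sentence is simply false. It fails only when read across the whole battery, which is how the rule operates. The sample-size reason fails on either reading.
- **Adjusting for a chance-imbalanced variable can help if it is prognostic.** In the simulation with r = 0.5, the spread of the estimate fell from 0.919 to 0.895 under the plan's rule, but to 0.796 with the covariate prespecified.

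**Conclusion.** The point holds as a limited one. The sample-size rationale is wrong, and a rule based on baseline p-values selects sensitivity covariates by chance imbalance and not by prognosis. As a result the adjusted model cannot be specified in advance, has no content from this rule when no test is positive, and seldom includes any particular prognostic variable.

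At least one positive test is roughly as likely as not: 40% to 64% for 10 to 20 independent tests, and about 37% to 50% for 17 under the correlated scenarios simulated. These figures are illustrative. They rest on an assumed 0.05 level, an assumed number of characteristics, and assumed correlations and site differences.

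The consequence is modest: average shifts below 0.2 points against a standard error of 0.92 and a target of 2.60, in one sensitivity analysis among several. It is worth correcting because correction is nearly free, not because the trial's main conclusion is at risk.

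**What to change.** In Section 9.1 C:

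1. Delete the sample-size rationale.
2. Remove baseline significance tests as the rule for choosing covariates, and report baseline data descriptively by arm. Summaries by treatment group are already planned.
3. Name the covariates for the adjusted sensitivity analysis now, on prognostic grounds, from variables that the documents show are available: site (Section 3.1 B), age and qualifying diagnosis (Section 3.2), inpatient versus post-discharge baseline, FRAIL score and PHQ-9 (Section 7.2). Add sex and days since the event if they are recorded; the documents do not list them as study variables. The documents do not show that this set predicts AM-PAC change, so the investigators should confirm it on clinical grounds before any outcome comparison by arm.

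Where PHQ-9 or FRAIL is itself the outcome, its baseline value is already in the model and need not be added again.

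The cost is a wording change and a few degrees of freedom out of about 298 completers. No new data collection is needed for the core list, and the primary analysis stays as written.
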